9.1. Height and Weight

Height and weight measurements will be performed as per the site's SOPs. Participants will be weighed on a calibrated scale at specified visits.

9.2. Biometric Measurements

Blood pressure, heart rate, and temperature will be measured at each visit. All measurements will be done according to the site's applicable SOP. Calibrated equipment will be used at every visit. Manual measurements may be taken for particular parameters where required by the PI and/or delegate.

9.3. Urine Sample Collection

A urine pregnancy test will be done for females of childbearing potential at Visit 1. If any pregnancies arise the participant will be screen-failed and therefore not be enrolled in the study.

9.4. Blood Sample Collection

Blood draws will be done for participants at all visits. Blood will be drawn by delegated site personnel from the antecubital site into the appropriate vacutainers as per the schedule of assessments, study visit details, and in accordance with the site's SOPs. The samples will be stored and/or sent for analysis as indicated in the Laboratory Manual. The total volume of blood to be collected (for safety parameters) from each participant over the course of the trial is 240 millilitres (approximately 16 tablespoons) and approximately 48 mL from each participant at each visit.

9.5. Questionnaires

- Total Nasal Symptoms Score (TNSS) Questionnaire: a method developed to assess allergic rhinitis symptoms, based on the administration of a questionnaire [33]. According to this method, allergic rhinitis symptoms are scored from 0 to 3 (4 grades of severity), and the differences between groups will be statistically assessed.

9.6. Peak Nasal Inspiratory Flow (PNIF) measurement

The assessment of allergic rhinitis [34]. Using this method (PNIF manual), the nasal volume and flow for assessing nasal airway patency will be measured.

9.7. Amplicon Metagenomics Sequencing Collection

This rRNA gene sequencing method would allow for the assessment of the effect of the treatment on the microbial diversity in saliva. Previous evidence has been given to suggest that allergic rhinitis may be associated with dysbiosis of the oral microbiota [16], [17], [18]. Changes in the parameters of microbiota will be analyzed.

9.8. Compliance

The participant will receive counselling and reminders pertaining to IP compliance and protocol requirements from delegated research site personnel.

Each participant will be required to complete a daily study diary to record the daily intake of the IP, concomitant medications, and record the occurrence of any adverse events. The participant will be required to return the IP to the research site for the IP compliance calculation using the following formula:

$$(\%) \text{ as } [(doses \text{ taken}/doses \text{ intended}) \times 100]$$

In the event the IP is returned to the study site compliance outside of 80-120% will be treated as a protocol deviation.

This compliance calculation will only apply to Visit 3.

9.9. Laboratory Analysis

All laboratory samples will be collected, processed, and stored until shipment or destruction by delegated personnel.

9.9.1. Endpoint-Related Samples

The following endpoints will be collected for each visit during the trial life cycle:

- V1-screening: Vital signs (Body temperature, blood pressure, and heart rate) will be measured and Blood Clinical Chemistry samples will be collected. Total Nasal Symptoms Score (TNSS) will be administered. A physical examination will be completed.
- V2-Baseline (D1): Total Nasal Symptoms Score (TNSS), Peak Nasal Inspiratory Flow (PNIF) values, Saliva sample collection for Amplicon Metagenomics Sequencing test, Vital signs (Body temperature, blood pressure, and heart rate) will be measured and Blood Clinical Chemistry samples will be collected.
- V3- Follow up (D7): Total Nasal Symptoms Score (TNSS), Peak Nasal Inspiratory Flow (PNIF) values, Saliva sample collection for Amplicon Metagenomics Sequencing test, Vital signs (Body temperature, blood pressure, and heart rate) will be measured and Blood Clinical Chemistry samples will be collected.
- V4- Follow up: Total Nasal Symptoms Score (TNSS), Peak Nasal Inspiratory Flow (PNIF) values, and Vital signs (Body temperature, blood pressure, and heart rate) will be measured.
- V5- End of study (D21): Total Nasal Symptoms Score (TNSS), Peak Nasal Inspiratory Flow (PNIF) values, Saliva sample collection for Amplicon Metagenomics Sequencing test, Vital signs (Body temperature, blood pressure, and heart rate) will be measured and Blood Clinical Chemistry samples will be collected.

9.9.2. Clinical Chemistry

Clinical chemistry parameters will be analyzed by a local analytical laboratory. For each laboratory parameter, results will be assessed by the PI. All in-study out-of-range and clinically significant laboratory results will be identified on the lab report by the analytical laboratory and/or PI and documented as adverse events, as applicable.

9.10. Termination of the Trial

The trial may be terminated at any time by the Sponsor, PI, or applicable regulatory authority (Health Canada and/or IRB). If the trial is terminated prematurely, the PI, participants, and the regulatory authorities must all be notified of the termination promptly. Upon termination of the trial whether premature, or due to completion, site-closeout activities will be initiated including regulatory closeout to the appropriate authorities.

10. Safety Instructions and Guidance

10.1. Adverse Events

Definition:

An unexpected event (i.e., medical occurrence, sign, or symptom) that happens during the study period with an investigational product. Adverse event (AE) may be mild, moderate, or severe, and may be caused by something other than the drug or therapy being given. Adverse events must be followed-up to resolution or when the condition is deemed stable by the PI.

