 - Serum creatinine
 - Potassium
 - Chloride
 - Sodium
 - IgE (total)
8. Be provided with a paper/electronic diary – IP dosing, adverse events, concomitant medication.
9. Be provided with the IP (and oral hygiene kit if applicable) and instructions on dosing.
10. Be provided with dates/times of subsequent visit(s).
11. Review of all information for the visit by the PI and/or delegate prior to the next study visit to determine continued safe participation.

The participant will be given a paper/electronic daily diary in order to record the use of concomitant medications, IP dosing, symptoms, and any adverse events (such as fatigue, fever or headache) that may have occurred. The diary will be collected and/or reviewed at the research site at each visit as indicated on the Schedule of Assessments.

The participant should take the IP after this visit at home. The participant should take AllerPops at a maximum frequency of once every other day until the next study visit (Day 7). The participant should not take the product the morning of the next visit. The designated maximum dose until the next visit on day 7, is 3 doses.

Visit 3 – Follow-Up – Day 7 ± 1

These assessments may not be completed in the order shown below.

Participants:

1. Must be at least 8 hours fasting (no food, only water) prior to visit.
2. Will have any changes to health reviewed by delegated study staff.
3. Study diary will be collected and/or reviewed by delegated study staff for completion, and any AEs and/or concomitant medications.
4. For females of childbearing potential, a urine sample will be collected for a urine pregnancy test.

5. Will have the following measurements taken: temperature, blood pressure, heart rate.
6. Will have the following saliva test:
 - Amplicon Metagenomics Sequencing
7. Will complete the following assessments:
 - Total nasal symptoms score (TNSS) questionnaire
 - Peak nasal inspiratory flow (PNIF) measurement
8. Will have the following blood tests:
 - CBC (WBC, RBC, Hb, HCT, MCV, MCH, MCHC, Platelet Count)
 - Aspartate aminotransferase (AST)
 - Alanine aminotransferase (ALT)
 - Bilirubin
 - Gamma-glutamyl transferase (GGT)
 - Alkaline phosphatase (ALP)
 - Serum creatinine
 - Potassium
 - Chloride
 - Sodium
 - IgE (total)
9. Be reminded to complete daily diary.
10. Review of all information for the visit by the PI and/or delegate prior to the next study visit to determine continued safe participation.

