After completion of treatment dose, the participants are allowed for extra 4 maintenance doses, at a maximum frequency of once every other day (on day 7, 9, 11, and 13). Participant will not take the product on day 14 and onwards, and must return all remaining product at visit 4. Between day 7 and day 13, the participants may take AllerPops with any recurrence of nasal allergy symptoms or until the participant is satisfied with the relief of the nasal allergy symptoms, as long as the minimal interval of alternate day dosing is not violated. The participant will continue to fill out a daily diary to indicate the time of dosing, symptoms, AEs (such as fatigue, fever or headache), and concomitant medications, if applicable.

Visit 4 – Follow-Up – Day 14 ± 2

These assessments may not be completed in the order shown below.

Participants:

1. Do not need to fast prior to this visit.
2. Will have any changes to health reviewed by delegated study staff.
3. Study diary will be collected and/or reviewed by delegated study staff for completion, and any AEs and/or concomitant medications.
4. Will have the following measurements taken: temperature, blood pressure, heart rate.
5. Will complete the following assessments:
 - Total nasal symptoms score (TNSS) questionnaire
 - Peak nasal inspiratory flow (PNIF) measurement
6. Be reminded to complete daily diary.

The participant will continue to fill out a daily diary to indicate symptoms, AEs (such as fatigue, fever or headache), and concomitant medications, if applicable.

After this visit, the participant will not continue taking the IP. Any remaining IP will be collected from the participant at this visit.

Visit 5 – End of Study – Day 21 ± 2

These assessments may not be completed in the order shown below.

Participants:

1. Must be at least 8 hours fasting (no food, only water) prior to visit.
2. Will have any changes to health reviewed by delegated study staff.
3. Study diary will be collected and reviewed by delegated study staff for completion, and any AEs and/or concomitant medications.
4. For females of childbearing potential, a urine sample will be collected for a urine pregnancy test.
5. Will have the following measurements taken: temperature, blood pressure, heart rate.
6. Will have the following saliva test:
 - Amplicon Metagenomics Sequencing
7. Will complete the following assessments:
 - Total nasal symptoms score (TNSS) questionnaire
 - Peak nasal inspiratory flow (PNIF) measurement

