10.2. Collecting, Recording, and Reporting of AEs

Collection:

The PI of delegated study staff must record all adverse events in an AE form with information about:

- Details of adverse event
- Date of onset (time can be recorded, if applicable)
- Intensity (mild, moderate, severe)
- Causal relationship to trial involvement (probable, possible, unlikely, not related)
- Other actions taken
- Date and time of outcome
- Outcome

Reporting:

The following timelines apply to the reporting of AEs/SAEs as applicable:

- Within 24 hours of the PI becoming aware of the event if it results in death of a participant

- Within 2 weeks (10 business days) after becoming aware of the event if:
 - It is an AE which is related to the conduct of the study;
 - It is an AE that is expected (listed in the ICF as a potential side effect) but is occurring more frequently than expected;
 - It is an unexpected AE/SAE that is related to the conduct of the study but is not life-threatening
- Annually (together with the Study Status Report) if:
 - It is an expected AE (listed in the ICF as a potential side effect);
 - It is an unexpected AE that is unlikely to be related to the conduct of the study and is not life-threatening.

Severity Assessment

All clinical events will be graded as mild, moderate, or severe according to the following scale:

Mild - The adverse event does not interfere in a significant manner with the subject's normal functioning level.

Moderate -The adverse event produces some impairment of functioning but is not hazardous to the subject's health.

Severe -The adverse event produces significant impairment of functioning and may be potentially hazardous to the subject's health.

Causality Assessment:

Certain – An adverse event that cannot be explained by disease or any other drugs.

Probably/Likely – An adverse event that follows a known, expected or suspected response pattern of the drug and is unlikely to be explained by any other factors or another etiology.

Possible – An adverse event that follows a known, expected or suspected response pattern of the drug but could readily have been produced by a number of other factors or explained by another etiology.

Unlikely – An adverse event that does not follow a known, expected, or suspected response pattern of the drug and could readily have been produced by a number of other factors or explained by another etiology.

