15.3. Risks and Procedures to Minimize Risk

Potential risks are disclosed to the study participants in the ICF prior to their participation in the study. The potential risks associated with the study include venipuncture and associated risks. The risks of venipuncture (at the site) include:

- Pain
- Bruising
- Infection

All venipuncture will be performed by certified phlebotomists and all applicable procedures will be carried out to minimize risk of infection.

The major active ingredient in the product, L-Arginine (402.81mg per dosage unit), does not affect endocrine, hepatic or renal function and can be safely used in adults. However, the individual with or at risk of cancer are excluded due to possible increased risk of adverse event occurrence.

The potential risks associated with the study product include development of low-grade fever, feeling tiredness or low-energy, and mild headache. Emergence of adverse events will be assessed at each visit.

16. Quality Assurance and Quality Control

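### Section 10.1 limits adverse events to unexpected ones, against the diary and section 10.2; and section 10.2 holds two causality lists that judge different things

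*Combined protocol and SAP*

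**What the plan says.** **Definition.** Section 10.1 describes an AE as "An unexpected event (i.e., medical occurrence, sign, or symptom) that happens during the study period with an investigational product".

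**Listed risks.** Section 15.3 says that potential risks are disclosed in the consent form, and continues: "The potential risks associated with the study product include development of low-grade fever, feeling tiredness or low-energy, and mild headache".

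**Diary.** Under Visit 2 in section 8, participants are to record "any adverse events (such as fatigue, fever or headache) that may have occurred". The instructions after Visits 3 and 4 repeat the examples: "AEs (such as fatigue, fever or headache), and concomitant medications, if applicable".

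**Reporting of expected events.** Section 10.2 has two rules. One, on the two-week timeline, reads: "It is an AE that is expected (listed in the ICF as a potential side effect) but is occurring more frequently than expected". The other, on the annual timeline, reads: "It is an expected AE (listed in the ICF as a potential side effect".

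**Causality.** The section 10.2 list of items to record for each AE includes "Causal relationship to trial involvement (probable, possible, unlikely, not related". Later the same section defines six levels: certain, probably/likely, possible, unlikely, conditional/unclassified and un-assessable/unclassifiable. The middle three are defined by the response pattern of the drug, and the top one reads: "An adverse event that cannot be explained by disease or any other drugs".

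**Analysis.** Safety is the first secondary objective, and the emergence of AEs is one of its measures (section 4). Section 11.3.4 says that AEs will be assessed, but plans no table by causality or by expectedness.

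**The concern.** Section 10.2 requires every AE to be recorded, and section 10.1 decides what an AE is. If the definition is applied as worded, staff could leave the product's known risks off the AE record. Other staff, following the diary and section 10.2, would record them. Both could cite the protocol. Vital signs may pick up a fever at a visit, but neither vital signs nor laboratory tests capture tiredness or headache, so those two depend mainly on AE collection.

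The causality lists raise a different question: whether an event is called related, and therefore when it is reported. For an unexpected event that is not life-threatening, section 10.2 chooses between two weeks and the annual report according to relatedness to the conduct of the study. Neither list says which of its levels count as related.

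**Working it through.** The plan states no figure on this point, so the check is a comparison of texts and a count of levels.

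**Step 1: are the listed risks expected in the protocol's own sense?** Section 10.2 explains expected as listed in the consent form as a potential side effect. Section 15.3 names three product risks and says that potential risks are disclosed in the consent form. All three are therefore expected.

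**Step 2: what does each place do with them?**

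| Place | Fever, tiredness, headache |
|---|---|
| 10.1 definition | Not AEs, read literally (3 of 3 left out) |
| Section 8, diary from Visit 2 and after Visits 3 and 4 | Named as examples of AEs |
| 10.2, two-week rule | AEs whose frequency must be followed |
| 10.2, annual rule | AEs to be reported |

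The two-week rule cannot operate unless expected events are counted. The definition is thus the odd one out.

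**Step 3: compare the causality lists**, treating *probable* and *probably/likely* as the same level.

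| Level | Collection list | Defined scale |
|---|---|---|
| Certain | no | yes |
| Probable | yes | yes |
| Possible | yes | yes |
| Unlikely | yes | yes |
| Not related | yes | no |
| Conditional/unclassified | no | yes |
| Un-assessable/unclassifiable | no | yes |

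The collection list has 4 levels and the scale has 6. Three are shared. That leaves 4 − 3 = 1 level collected but undefined, and 6 − 3 = 3 levels defined but not in the collection list.

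**Step 4: what is being judged?** The collection list asks about trial involvement, and the reporting rules ask about the conduct of the study. The scale is framed around the drug. In many trials the gap would be small. Here both arms take the same product (sections 3 and 6.4). The investigational arm brushes, scrapes the tongue (with a caution about gagging) and gargles hot water before dissolving the lozenge. The control arm microwaves it, cuts it up and swallows the pieces.

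Take an event caused by one of these steps. Judged against trial involvement, it could be *probable*. Judged against the drug's response pattern, with another ready explanation, it points to *unlikely*. Yet the top level rules out only disease and other drugs, so read literally the same event might meet *certain*. The scale was not written for procedural causes.

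**Step 5: which outputs are affected?**
- The definition can affect the number of non-serious AEs recorded. Serious AEs have their own definition in section 10.3, which is not limited to unexpected events.
- The causality mismatch cannot affect the number of AEs. It can affect relatedness and the choice between two-week and annual reporting. The annual rule covers unexpected events that are unlikely to be related, and the two-week rule covers related ones. The level *possible* is assigned to neither.

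**The case against.** The strongest reply is that the operating text overrides a loosely chosen word. The diary asks for exactly these symptoms. Section 10.2 has rules for expected AEs, and its causality definitions speak of expected response patterns. AE assessment is scheduled at Visits 2 to 5 (section 2.3). If *unexpected* were a filter, both rules on expected AEs would have nothing to act on, so the coherent reading is that it is not meant as one.

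Most of this stands. A reader might infer that the listed risks will be dropped, that the AE count is biased downward, or that safety counts are unreliable. The documents do not support that: the diary prompts work against it, and nothing in the documents gives a rate or a direction that could be quantified. What the reply does not remove is the contradiction itself. The definition is still the rule to which staff turn when a case is doubtful.

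On causality, a reader might infer that the AE form cannot record a certain relationship. The form is not in the documents, and case report forms are to be created after the protocol is final (section 16.3.2). What is shown is a mismatch between two lists in one section. It is also fair to say that they may be meant as two separate judgements, one on the trial and one on the product. If so, the plan should say so, because merging them carelessly would lose procedure-related causality.

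**Conclusion.** Both conflicts are real and both are matters of wording.

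The section 10.1 definition, read literally, leaves out 3 of the 3 listed product risks and contradicts sections 8 and 10.2. The consequence is a risk of inconsistent recording and under-counting of expected, non-serious events for the first secondary objective. The diary prompts partly mitigate it, and the documents give no basis for putting a size on it.

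The two causality lists share three levels and judge different things. AE totals are unaffected, and no planned table depends on causality. Relatedness classification and the timing of reports can be affected, and this matters more than usual because the arms differ only in procedure.

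The conclusion assumes that *expected* has in section 10.1 the meaning that section 10.2 gives it, and that the consent form lists the three risks, as section 15.3 indicates. It does not touch the primary endpoint or the analysis set. The correction should be made because it is cheap and concerns a named objective and reporting duties.

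**What to change.** 1. In section 10.1, replace the reference to an unexpected event with: *any untoward medical occurrence during the study period, whether or not expected or related*. Section 10.3 already uses the untoward-occurrence wording for serious events.
2. Keep the study period as the window and flag each event as starting before or after the first dose. Narrowing the definition to events after first dose would be a mistake. Blood is drawn at Visits 1 and 2, the first dose is taken at home after Visit 2, and section 15.3 lists pain, bruising and infection from venipuncture as study risks.
3. In section 10.2, reconcile the two lists into one set of levels, each with a definition, and use it on the AE form.
4. State whether the product and the study procedures are judged together or separately.
5. State which levels count as related for the section 10.2 reporting rules, so that *possible* and any un-assessable level have a defined place.

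The cost is a few sentences of protocol text and a matching AE form. AE counts may be slightly higher than under a literal reading of the present definition.

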10.2. Collecting, Recording, and Reporting of AEs

Collection:

The PI of delegated study staff must record all adverse events in an AE form with information about:

- Details of adverse event
- Date of onset (time can be recorded, if applicable)
- Intensity (mild, moderate, severe)
- Causal relationship to trial involvement (probable, possible, unlikely, not related)
- Other actions taken
- Date and time of outcome
- Outcome

Reporting:

The following timelines apply to the reporting of AEs/SAEs as applicable:

- Within 24 hours of the PI becoming aware of the event if it results in death of a participant

- Within 2 weeks (10 business days) after becoming aware of the event if:
 - It is an AE which is related to the conduct of the study;
 - It is an AE that is expected (listed in the ICF as a potential side effect) but is occurring more frequently than expected;
 - It is an unexpected AE/SAE that is related to the conduct of the study but is not life-threatening
- Annually (together with the Study Status Report) if:
 - It is an expected AE (listed in the ICF as a potential side effect);
 - It is an unexpected AE that is unlikely to be related to the conduct of the study and is not life-threatening.

Severity Assessment

All clinical events will be graded as mild, moderate, or severe according to the following scale:

Mild - The adverse event does not interfere in a significant manner with the subject's normal functioning level.

Moderate -The adverse event produces some impairment of functioning but is not hazardous to the subject's health.

Severe -The adverse event produces significant impairment of functioning and may be potentially hazardous to the subject's health.

Causality Assessment:

Certain – An adverse event that cannot be explained by disease or any other drugs.

Probably/Likely – An adverse event that follows a known, expected or suspected response pattern of the drug and is unlikely to be explained by any other factors or another etiology.

Possible – An adverse event that follows a known, expected or suspected response pattern of the drug but could readily have been produced by a number of other factors or explained by another etiology.

Unlikely – An adverse event that does not follow a known, expected, or suspected response pattern of the drug and could readily have been produced by a number of other factors or explained by another etiology.

Conditional/Unclassified – An adverse event that requires more data for proper assessment or there is additional data under examination.

Un-assessable/Unclassifiable – An adverse event that cannot be judged because information is insufficient or contradictory.

